Among the primary disabilities resulting from stroke is motor impairment of the upper limbs, leading to partial or complete inability to move the affected limb. This impacts the ability to perform reaching tasks due to impaired motor coordination or an inability to control grip and finger strength during object manipulation (Steenbergen & Van Der Kamp, 2004). In daily life, this disability manifests as an inability to eat, dress, or attend to personal hygiene independently, resulting in dependence on a caregiver and negatively affecting the quality of life. Therefore, continuous rehabilitation to regain motor skills is vital for both the patient and their caregivers (Duncan et al., 1994).

From a neuroscientific perspective, movement planning, preparation, and execution deficits can result from damage to primary motor cortix area responsible for praxis control, or distorted body representation, altering proprioceptive and kinesthetic signals and the perception of peripersonal space (Wallwork et al., 2016). Consequently, patients may experience an altered the sense of embodiment, or the perception of their own body. Specifically, the sense of embodiment consists of three factors: a) ownership, the perception of possessing one's own body; b) agency, the perception of motor control over one's body; and c) location, the perception of being physically in the same place as the body. Together, these factors allow individuals to perceive, act, and interact in their surrounding environment (Kilteni et al., 2012).

Recent studies have shown that intervening through the illusion of corporeal self in hemiplegic patients improves the rehabilitation of the affected limb (Cha et al., 2021; Tambone et al., 2021). One of the systems used for generating the illusion of the limb is the mirror box, a tool in which the patient

embodies the healthy arm reflected in a mirror. If the illusion is successful, the patient perceives the reflected arm in the mirror as their own instead of the impaired limb (Ezendam et al., 2009). This may be possible because the embodiment of the reflected hand improves the reorganization of body representation in post-stroke patients with motor deficits (Tosi et al., 2018). Rehabilitation through limb illusion has been further translated into virtual reality, demonstrating its effectiveness in upper limb rehabilitation (Weber et al., 2019; Hsu et al., 2022).

In recent decades, virtual reality has been widely used in upper limb motor rehabilitation following a stroke, yielding significant results when compared to traditional rehabilitation programs (Holden et al., 2007; Kim et al., 2020). Virtual reality is an advanced technology that provides interactive environments replicating the surrounding reality. It is divided into immersive and non-immersive virtual reality; the former allows the patient to feel present in the virtual environment through a head-mounted display, while the latter projects the virtual environment onto a screen, and the patient interacts with it through devices such as joysticks or cybergloves (Henderson et al., 2007). In rehabilitation, virtual reality improves neuroplasticity and motor recovery by providing engaging training with real-time feedback, customization of exercises based on cognitive and motor abilities, immersive and interactive experiences, and faithful simulation of real-world activities (Turolla et al., 2013). However, the effectiveness of incorporating the illusion of one's limb into virtual reality rehabilitation is not yet fully understood.

Therefore, given the high incidence of stroke, the resulting disabilities, and the need for prompt and continuous rehabilitation, along with promising data on virtual reality as an effective tool for sensorimotor and proprioceptive rehabilitation, this project aims to study the efficacy of a virtual reality system for upper limb rehabilitation using the corporeal self-illusion paradigm.

1.1. Study hypotheses

This study is based on the hypothesis that a neurorehabilitation protocol utilizing virtual reality will be effective in the sensorimotor and proprioceptive rehabilitation of the upper limb in patients with post-stroke outcomes. Additionally, it is hypothesized that administering a rehabilitation protocol with virtual reality may prove more effective than the traditional rehabilitation protocol administered in routine clinical practice for recovering sensorimotor and proprioceptive deficits in the upper limb of patients with post-stroke outcomes.

1.2. Study aim

The primary aim of this study is to assess the effectiveness of a neurorehabilitation protocol using a virtual reality system for recovering sensorimotor and proprioceptive deficits in the upper limb of patients with post-stroke outcomes.

The secondary objective is to compare the outcomes, defined as the recovery of sensorimotor and proprioceptive function in the upper limb, between patients undergoing rehabilitation with virtual reality and those undergoing standard upper limb rehabilitation as per routine clinical practice.

2. Study objectives

2.1. Primary abjective

Assessing the effect of a rehabilitation protocol using a virtual reality system for the recovery of sensorimotor and proprioceptive function in the upper limb in patients with stroke outcomes.

2.2. Secondary objective

- Comparing the outcomes of a rehabilitation protocol using virtual reality against the standard rehabilitation protocol administered as per normal clinical practice for the recovery of sensorimotor and proprioceptive function in the upper limb in patients with stroke outcomes.
- Assessing the satisfaction of patients with stroke outcomes regarding the implementation of an upper limb rehabilitation program conducted with virtual reality.

3. Material and method

3.1. Study design

Randomized control trial without pharmaceuticals use.

3.2. Population

Inclusion criteria:

- Age between 18 and 85 years;
- Female and male;
- Diagnosis of stroke outcomes occurring between 2 months and 18 months prior to enrollment;
- Impairment of upper limb functionality (Motricity Index with total score for the upper limb ≤ 80);
- Sensorimotor and proprioceptive impairment of the upper limb (Negative Thumb Location Test in 3 out of 4 trials);
- Signed informed consent to participate in the study.

Exclusion criteria:

• Ongoing clinical instability;

- Severe psychiatric comorbidity that may interfere with adherence to the proposed treatment protocol (e.g., severe personality disorders, severe psychomotor agitation);
- Severe impairments in upper limb motor function: Motricity Index Scale with the following cutoffs: pinch grip < 11, elbow flexion < 14, shoulder abduction < 14;
- Severe deficit in verbal comprehension: Token Test (Spinnler 1987) with a score < 2;
- Severe spatial neglect: Barrage Test (Albert 1973) score > 3.

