3.3. Procedure

Patients who meet the inclusion criteria, in the absence of all exclusion criteria, will be recruited at the Department of Rehabilitation Medicine and Neuro-rehabilitation (SC) of IRCCS Institute of Neurological Sciences in Bologna after signing the informed consent. For recruitment purposes, the Principal Investigator (PI) or a delegate will explain to the patient the rationale and operational procedures of the study using the information provided in the study information sheet. After enrollment, the included patients will be randomized into two groups: a treatment group (VR) that will undergo upper limb rehabilitation for proprioceptive and sensorimotor recovery using the Khymeia system with virtual reality exercises, and a control group (C) that will undergo upper limb rehabilitation according to standard clinical practice. Both groups will receive the same number of rehabilitation sessions with the same duration and weekly frequency for the recovery of sensorimotor and proprioceptive function in the upper limb. If included patients need to undergo a rehabilitation protocol for the recovery of other deficits related to the stroke event (e.g., language disorders, dysphagia, hemiplegia of the lower limbs, gait abnormalities), the execution of the rehabilitation pathway will be ensured according to standard clinical practice for those disorders.

The randomization list will be generated by the PI before the start of the study using Microsoft Excel and kept by an investigator not involved in patient assessment. Patients will be assigned to the two groups following the randomization sequence. Subsequently, patients in both groups will undergo pre-test evaluations (T0).

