5.1. Sample size

This study plans to enroll 20 patients, with 10 in the experimental group (VR) and 10 in the control group (C). Given that the study duration is 24 months, with the last 6 months dedicated to statistical analysis, results analysis, and scientific dissemination, the active recruitment and patient inclusion period is estimated to be 18 months. Each patient will participate in the study for 6 weeks (1 week for the baseline assessment at T0, 4 weeks for rehabilitation, and 1 week for the post-treatment assessment at T1). It is believed that the overall number of 20 included patients is achievable within the study's timeframe.

As this is a pilot study, the sample size is considered sufficient to achieve the set objectives, taking into account a potential dropout rate of 20%.

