5.2. Statistical analysis

The data analysis will be conducted using the Statistical Package for Social Science (SPSS version 26.0).

The preliminary data obtained from the pilot study will allow for estimating the variation in outcome measures between pre-test and post-test and between the treatment and control groups, providing insights for a potential subsequent trial with a larger sample.

The data will be analyzed based on the stated objectives, which include:

- Descriptive analysis of socio-demographic data for the experimental and control groups, including mean and standard deviation.
- The effect of the virtual reality rehabilitation protocol in the treated group will be assessed by comparing the scores of evaluation scales at pre-test and post-test. Data distribution will be tested using the Shapiro-Wilk test. The non-parametric Friedman test will be used in case of non-normal distribution, while ANOVA will be utilized in case of normal distribution. The significance level will be defined at $p \le 0.05$.
- The effect of the virtual reality rehabilitation protocol compared to the standard rehabilitation protocol will be assessed by comparing the scores of scales at T0 and T1 between the VR and C groups using the non-parametric Mann-Whitney test for independent samples.

6. Relevance

If the experimental hypotheses will be confirmed, the use of the virtual reality rehabilitation system could be implemented in routine clinical practice to rehabilitate sensorimotor integration in patients with stroke outcomes. An innovative approach employing virtual reality techniques aims not only to enhance patient treatment adherence but also to support proprioceptive and sensorimotor rehabilitation through the body illusion paradigm, which is not achievable in traditional rehabilitation. The enhancement of proprioceptive and sensorimotor aspects is considered crucial for the rehabilitation of neuromotor impairment. Therefore, by promptly implementing this type of intervention following a cerebrovascular event, one could hope for a faster and more effective functional recovery.

7. Feasibility

• The Rehabilitation Medicine and Neuro-rehabilitation Unit of the IRCCS Institute of Neurological Sciences in Bologna coordinates both the acute rehabilitation phase (with daily consultations at the Stroke Unit) and the sub-acute phase of the Stroke Clinical Pathway. Consequently, they daily admit patients with stroke outcomes at various stages of the

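### Time since stroke (2 to 18 months) is neither balanced in the allocation nor accounted for in the VR-versus-control test, so a chance imbalance can shift the secondary between-arm estimate

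*Protocol*

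**What the plan says.** Section 3.2 sets the entry window: "Diagnosis of stroke outcomes occurring between 2 months and 18 months prior to enrollment". Section 5.1 plans 20 patients, 10 in each arm, and allows for 20% dropout.

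On allocation, section 3.3 says that "The randomization list will be generated by the PI before the start of the study using Microsoft Excel" and then that "Patients will be assigned to the two groups following the randomization sequence". It names no stratum, block or minimisation factor. The T0 battery follows assignment, but time since stroke is an entry criterion and so is known beforehand.

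On analysis, section 5.2 compares scale scores at T0 and T1 "between the VR and C groups using the non-parametric Mann-Whitney test for independent samples". No covariate or stratum is attached to that test. The same section says that the pilot should help estimate variation between the groups for a possible larger trial. Sections 2.2 and 4.2 make the VR-versus-control comparison secondary.

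Two remarks bear on stage. Section 6 says that "by promptly implementing this type of intervention following a cerebrovascular event, one could hope for a faster and more effective functional recovery". Section 7 says that the unit's patients are at differing points in their rehabilitation.

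**The concern.** The latest eligible patient is nine times as far from the stroke as the earliest (18 / 2 = 9). If patients nearer the stroke change more over the treatment period whatever they receive, an arm that happens to get more of them will look better. That can create an apparent VR advantage or hide a real one. Ten patients per arm is too few to rely on randomisation to even this out, and neither the list nor the test makes up for it.

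Adjusting for the T0 score alone would not settle the matter, since two patients with equal T0 scores at 2 and 17 months may still have different expected change. What is at stake is the only randomised contrast in the trial, and the between-group figures that are meant to inform a later one.

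**Working it through.** **Inputs from the protocol:** 20 patients, 10:10 (5.1); window of 2 to 18 months (3.2); 20% dropout (5.1); Mann-Whitney test (5.2); significance at 0.05, stated in 5.2 under the within-VR analysis and taken here as two-sided.

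**Assumptions not in the protocol:** the share of early patients; an early-late gap in spontaneous change of 0.5, 1.0 or 1.5 within-stage SD; analysis of change scores.

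**The plan's own figure.** The sample size rests on feasibility and pilot status. With no effect size, SD or power given, 20 cannot be derived. The dropout allowance gives 20 × 0.8 = 16 completers.

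**Chance of imbalance.** With K early patients among 20 and 10 going to VR, the number of early patients in VR is hypergeometric: P(k) = C(K,k) × C(20−K,10−k) / C(20,10), where C(20,10) = 184,756.

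- K = 10: P(5) = 252² / 184,756 = 0.344, and P(4) = P(6) = 210² / 184,756 = 0.239. So P(7:3 or worse) = 1 − 0.344 − 2 × 0.239 = 0.18 (0.179 unrounded).
- K = 8: P(difference of 4 or more) = 2 × (13,860 + 1,760 + 66) / 184,756 = 0.170.
- K = 6: P(difference of 4 or more) = 2 × (12,012 + 1,001) / 184,756 = 0.141.
- 16 completers, 8 of them early: P(6:2 or worse) = 0.13.

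Without a cut-point, and assuming months since stroke are uniform on 2 to 18, the SD of the difference in arm means is (16/√12) × √(2/10) = 2.1 months. The chance of a difference of at least 3 months is 0.15, and of at least 4 months 0.05.

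**Shift in the estimate.** At 7:3 the shift is (0.7 − 0.3) × gap, that is 0.2, 0.4 or 0.6 SD for gaps of 0.5, 1.0 or 1.5 SD.

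**Effect on the planned test** (40,000 simulated trials per setting, 10 of 20 early, 1 SD gap):

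| Early patients, VR v control | Rejection rate, no true effect | Rejection rate, true 1 SD effect |
|---|---|---|
| 3 v 7 | 0.087 | 0.15 |
| 5 v 5 | 0.026 | 0.41 |
| 7 v 3 | 0.085 | 0.73 |
| All allocations | 0.044 | 0.42 |

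At a 0.5 SD gap, the false-positive rate when the early patients split 7:3 either way is only 0.05 to 0.06.

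**Precision.** With half the patients early, leaving stage out multiplies the variance of change by 1 + 0.25 × gap² = 1.06, 1.25 or 1.56. For a 1 SD gap the SD becomes √1.25 = 1.118. Approximate power for a true 1 SD effect is Φ(1 / (SD × √(2/10)) − 1.96):

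- stage left in (SD 1.118): Φ(2.00 − 1.96) = 0.52
- stage removed (SD 1): Φ(2.236 − 1.96) = 0.61

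**Stratifying without changing the test.** With a forced 5:5 split and a 1 SD gap, the unadjusted Mann-Whitney has type I error of 0.024 and power of 0.41, against 0.044 and 0.42 without stratification. The test becomes conservative and gains no power.

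**The case against.** A reader might infer that the comparison is biased or that its error rate is inflated. The documents do not support that. Allocation is random, and over all allocations the simulated type I error is 0.044. A split of 7:3 or worse is avoided about 82% of the time even when half the patients are early. Any unbalanced covariate in 20 patients adds sampling error of this kind. This objection stands, and it limits the point to conditional imbalance and precision.

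A reader might also infer that the protocol itself treats time since stroke as prognostic. It does not go so far. Section 6 voices a hope about prompt use of the intervention, and section 7 is about patient supply. They suggest that timing matters but give no size for it. The protocol also does not rank this variable above age (18 to 85) or Motricity Index, which are equally unstratified.

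Three further limits stand. The absence of stratification is read from silence, together with the wording of one list and one sequence. The 0.4 × gap result assumes change scores, whereas 5.2 speaks only of scores at T0 and T1. The contrast is secondary, in a pilot, and nothing here touches the within-VR primary analysis.

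It is fair to add that adjustment is often left to an SAP, which is not shown. But the protocol does name its between-arm test, and an allocation list cannot be repaired once patients are enrolled.

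**Conclusion.** The point holds as a matter of chance imbalance and lost precision in a secondary comparison. With half the patients early, there is an 18% chance of a 7:3 or worse split, and at 7:3 the VR-versus-control difference moves by 0.2 to 0.6 SD for gaps of 0.5 to 1.5 SD. Ignoring stage also lowers approximate power from 0.61 to 0.52 for a true 1 SD effect with a 1 SD gap. These sizes depend on an early share and a gap that the protocol does not supply. At the low end of the range the effect on false positives is slight. The case for acting is that the variable is already collected at entry and the between-arm estimate is meant to feed a later trial. Nothing here shows that the eligibility window is wrong.

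**What to change.** **Section 5.2.** Replace the unadjusted VR-versus-control comparison with one that accounts for time since stroke. One option is a linear model (ANCOVA) of the T1 score on arm, T0 score and time since stroke, which gives an estimate with a confidence interval. If a rank test is kept, use a van Elteren test stratified by early/late. It yields a p-value rather than an estimate, and would work with about 5 patients per cell, or 4 after 20% dropout. Report time since stroke by arm in either case.

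**Section 3.3.** Together with that change, and not alone, stratify the Excel list by one early/late cut-point fixed before enrolment. Use small permuted blocks of stated size, concealed from those who recruit. Since 3.3 has the PI generate the list and also allows the PI to recruit, someone who does not recruit would need to set the blocks.

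**Cost.** A second list and a changed analysis sentence, with no extra patients or visits. The model uses one or two degrees of freedom. Arms may not end exactly 10:10: each of the two strata can finish one patient apart with blocks of 2 (up to 11:9 overall) or two apart with blocks of 4 (up to 12:8). Small blocks make assignments slightly more predictable. A cut-point fixed in advance does not guarantee equal numbers of early and late patients.

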3.3. Procedure

Patients who meet the inclusion criteria, in the absence of all exclusion criteria, will be recruited at the Department of Rehabilitation Medicine and Neuro-rehabilitation (SC) of IRCCS Institute of Neurological Sciences in Bologna after signing the informed consent. For recruitment purposes, the Principal Investigator (PI) or a delegate will explain to the patient the rationale and operational procedures of the study using the information provided in the study information sheet. After enrollment, the included patients will be randomized into two groups: a treatment group (VR) that will undergo upper limb rehabilitation for proprioceptive and sensorimotor recovery using the Khymeia system with virtual reality exercises, and a control group (C) that will undergo upper limb rehabilitation according to standard clinical practice. Both groups will receive the same number of rehabilitation sessions with the same duration and weekly frequency for the recovery of sensorimotor and proprioceptive function in the upper limb. If included patients need to undergo a rehabilitation protocol for the recovery of other deficits related to the stroke event (e.g., language disorders, dysphagia, hemiplegia of the lower limbs, gait abnormalities), the execution of the rehabilitation pathway will be ensured according to standard clinical practice for those disorders.

The randomization list will be generated by the PI before the start of the study using Microsoft Excel and kept by an investigator not involved in patient assessment. Patients will be assigned to the two groups following the randomization sequence. Subsequently, patients in both groups will undergo pre-test evaluations (T0).

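### Allocation concealment is not protected: the PI generates the whole list and may also recruit, and no concealed release of assignments is stated

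*Protocol*

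**What the plan says.** Everything on allocation is in Protocol section 3.3 (Procedure).

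- **Who makes the list:** "The randomization list will be generated by the PI before the start of the study using Microsoft Excel".
- **Who keeps it:** the list is "kept by an investigator not involved in patient assessment".
- **Who recruits:** "For recruitment purposes, the Principal Investigator (PI) or a delegate will explain to the patient the rationale and operational procedures of the study".
- **When patients are randomised:** "After enrollment, the included patients will be randomized into two groups".
- **How assignments are released:** "Patients will be assigned to the two groups following the randomization sequence". No envelope, central service or other concealed step is described.
- **Baseline testing:** the T0 assessments come after assignment.

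Section 5.1 plans 20 patients, 10 per arm, with a possible dropout of 20%. Sections 2.2 and 4.2 make VR versus control a secondary objective and endpoint, and section 5.2 tests it with the Mann-Whitney test.

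**The concern.** Concealment requires that whoever decides whom to approach, and whether a patient enters, cannot know the next assignment. Section 3.3 gives the full sequence to its author, the PI, and names the same role first among those who may recruit. Passing the list to another investigator afterwards does not remove what its author has already seen. The restriction on the custodian separates custody from outcome assessment. It does not separate custody from recruitment, eligibility decisions or treatment.

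Foreknowledge has room to act. Section 3.2 excludes patients for clinical instability and for psychiatric comorbidity that might interfere with adherence, and both call for judgement. Eligibility runs from 2 to 18 months after stroke, so the order and timing of approach can also change the prognosis of the next patient entered. T0 follows assignment, so the T0 scores cannot serve as a clean check on whether entry was steered.

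At stake is the VR-versus-control comparison, the only contrast that randomisation supports. Section 5.2 intends the pilot's between-group variation to inform a larger trial, so a bias here would carry forward. Analysis cannot reliably remove it afterwards.

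**Working it through.** The protocol states no figure on this point, and section 5.1 justifies 20 patients by feasibility and pilot status. There is nothing to reproduce, so the check is a comparison of the text followed by two illustrations.

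**Step 1. Who can know the next assignment (section 3.3).**

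| Role | May know the list? | Barred from recruiting? |
|---|---|---|
| PI | Yes, generates it | No, named as a recruiter |
| Delegate of the PI | Not stated | No, named as a recruiter |
| Custodian | Yes, keeps it | No, barred only from assessment |

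Randomising after enrolment does not close the gap, because the sequence is fixed before the study starts.

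**Step 2. Predictability.** Assume a list of exactly 10 and 10 with no other restriction.

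- With the list in hand: up to 20 of 20 assignments known.
- Without the list, but seeing past assignments and always guessing the arm with more places left, the expected number of correct guesses is n + (4^n / C(2n,n) − 1)/2. With n = 10, 4^10 = 1,048,576 and C(20,10) = 184,756, so 10 + (5.6755 − 1)/2 = 12.34, or 12.34/20 = 61.7%.

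The fair comparator is therefore about 62%, not 50%. A figure of 50% would apply only if past assignments were also hidden or the list were unrestricted.

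**Step 3. What an imbalance would do to the test.** Inputs: 10 per arm less 20% dropout gives 10 × 0.8 = 8 per arm (section 5.1). The test is two-sided at 5%; section 5.2 states that level under the within-group analysis, and it is assumed here for the between-group test as well. Normally distributed outcomes and a spurious prognostic shift of 0.3 or 0.5 SD are assumptions; the protocol gives no such figure.

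The standard error of the difference in means at 8 per arm is √(2/8) = 0.5 SD, so the shifts equal 0.3/0.5 = 0.6 and 0.5/0.5 = 1.0 standard errors.

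| Test, per arm | No shift | 0.3 SD | 0.5 SD |
|---|---|---|---|
| Two-sample t, 8 | 0.050 | 0.087 | 0.154 |
| Exact Mann-Whitney, 8 (simulated, 20,000 runs) | 0.05 nominal | 0.087 | 0.149 |

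Repeating the Mann-Whitney simulation with 200,000 runs gave 0.085 and 0.148. Under the test that the protocol names, the false-positive rate rises from 5% to about 9-15%.

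**Step 4. What a fixed 10:10 list still reveals.** Once one arm is full, all remaining assignments are certain. The expected number is 2n/(n + 1) = 20/11 = 1.8.

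**The case against.** Several points on the other side are fair.

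- **The PI may not recruit.** A reader might infer that the person who makes the list is the person who enrols patients. The text permits this but does not establish it: a delegate may recruit, and the protocol does not say who confirms eligibility. This stands, and it limits the point to concealment not being protected. The text does not show that concealment will fail or that anyone will steer enrolment.
- **Most entry criteria are numeric.** Age, time since stroke, Motricity Index, Thumb Location Test, Token Test and Barrage Test leave little discretion over eligibility. This stands for eligibility, but not for whom to approach or when.
- **The comparison is secondary, in a pilot.** The primary endpoint is the change from T0 to T1, which section 5.2 analyses within the VR group. A reader might infer that a lapse in concealment undermines that analysis. It does not do so directly, because that analysis makes no use of randomisation. The between-group estimate is still the only one that randomisation supports, and it is meant to inform a larger trial.
- **The size is assumed.** Nothing in the protocol makes a shift of 0.3 to 0.5 SD likely. The rates show only what such a shift would do.
- **Blinding.** A reader might take the trial to be open throughout. The protocol does not describe blinding, so the point does not rest on that.

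It could also be said that concealment is a detail left to another document. That does not stand: the protocol itself gives the generation of the list to the PI.

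**Conclusion.** The point holds as a defect in a stated procedure. Section 3.3 lets one role both author the complete sequence and recruit, its custody safeguard does not cover recruitment, and it describes no concealed release. A person who may recruit can therefore know up to 20 of 20 assignments, against about 12.3 of 20 from past assignments alone in a 10:10 list.

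The secondary VR-versus-control comparison is exposed to selection bias. The rise in false positives to about 9-15% depends on an assumed imbalance of 0.3 to 0.5 SD with 8 per arm; it is an illustration, not an estimate of what will happen. The correction is cheap and has to be made before the list is generated.

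**What to change.** Change section 3.3 so that:

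1. The list is generated and held by one investigator with no part in recruitment, eligibility decisions, treatment or assessment. The custodian already named can do this if that person meets the condition; otherwise another existing team member is needed.
2. Neither the PI nor any recruiter sees the list.
3. Assignments are released one at a time, each only after consent and eligibility are recorded. Preferably T0 is also recorded first, so that baseline scores are obtained before the arm is known. This last part is a separate change, because T0 now follows assignment.

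**Cost.** A few sentences of text. It needs no change of personnel only if the custodian has no recruiting or treating role, which the protocol does not say. The list-holder must be reachable at each enrolment. With a fixed 10:10 list, anyone counting past allocations can still infer the last one or two assignments (1.8 on average). That leak is small beside knowledge of the whole list, but it should be acknowledged.

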4.1. Primary endpoint

In order to assess the effect that the proposed treatment has on the sensorimotor and proprioceptive impairment of the upper limb, a comparison is conducted between the baseline assessments (T0) and those performed at the end of the 4-week rehabilitation treatment (T1).

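### Baseline (T0) is taken after patients are assigned to VR or control, which leaves the T0-based efficacy comparisons open to an avoidable bias of unknown size and direction

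*Protocol*

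**What the plan says.** Section 3.3 (Procedure) gives the sequence. Consent and enrolment come first, and then "After enrollment, the included patients will be randomized into two groups". The list is "generated by the PI before the start of the study using Microsoft Excel and kept by an investigator not involved in patient assessment". The section ends: "Patients will be assigned to the two groups following the randomization sequence. Subsequently, patients in both groups will undergo pre-test evaluations (T0"). No other section places T0 before assignment. Section 5.1 gives only durations ("1 week for the baseline assessment at T0, 4 weeks for rehabilitation, and 1 week for the post-treatment assessment at T1"), which fit either order.

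T0 is then used in two places:

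- **Primary.** Section 4.1 says "a comparison is conducted between the baseline assessments (T0) and those performed at the end of the 4-week rehabilitation treatment (T1"). Section 5.2 carries this out in the VR group by "comparing the scores of evaluation scales at pre-test and post-test", with Friedman or ANOVA depending on normality.
- **Secondary.** Section 5.2 compares the arms by "comparing the scores of scales at T0 and T1 between the VR and C groups using the non-parametric Mann-Whitney test". It does not say whether the test is applied to change or separately at each time point.

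**The concern.** A baseline is protected by randomisation only if it is recorded before anyone can react to the allocation. Here it is recorded afterwards. A patient assigned to head-mounted-display exercises or to standard rehabilitation will know which, and section 3.3 does not say that the assignment is withheld until T0 is complete. Several T0 measures in section 3.3.3 depend on effort, self-report or rater judgement: Fugl-Meyer, FIM, MAIA and the Rubber Hand Illusion test are examples. Enthusiasm, disappointment or a rater's expectation could move them.

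A change score is T1 minus T0, so an error in T0 that differs between arms appears in the change with its sign reversed. Section 5.2 intends the data to inform a possible larger trial, and a distorted baseline would carry into that planning. There is also a missing-data consequence. A patient who withdraws on learning the arm would have no T0 values beyond the Motricity Index and Thumb Location Test, which section 3.2 requires for eligibility. The protocol does not say whether those eligibility values may serve as T0.

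**Working it through.** **What can be reproduced.** The protocol states no figure on this point. Its sample size (section 5.1: 20 patients, 10 per arm, 20% dropout) rests on feasibility and pilot status, with no effect size, SD or power to rederive. The dropout arithmetic is consistent: 20 × (1 − 0.20) = 16 completers, or 8 per arm if losses are equal. Reordering T0 changes none of this.

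**Which analyses a T0 shift reaches**

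| Analysis | Uses T0 scale scores? | Affected? |
|---|---|---|
| Within-VR, T0 against T1 (4.1, 5.2) | Yes | Yes |
| VR against C, if done on change (4.2, 5.2) | Yes | Yes |
| VR against C, if done at T1 alone | No | No |
| Satisfaction questionnaire (3.3.4, 4.2) | No, post-treatment only | No |
| Socio-demographic description (5.2) | No | No |

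**Illustration of size.** Inputs from the protocol: 10 or 8 per arm, and an alpha given as "The significance level will be defined at $p \le 0.05"$, taken as two-sided because sidedness is not stated. Assumed inputs, not in the protocol: normal scores with unit SD at both times, T0-T1 correlation r = 0.8, no true effect, and VR scores at T0 recorded b = 0.2 or 0.3 SD too low.

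1. SD of change = √[2(1 − r)] = √0.4 = 0.632.
2. Bias in the between-arm difference in mean change = b, that is 0.2 or 0.3 SD.
3. Standardised shift d = b / 0.632 = 0.316 or 0.474.
4. Two-sample t-test: noncentrality d√(n/2), df 2n − 2. Within-VR paired t-test (equivalent to a two-time-point repeated-measures ANOVA): noncentrality d√n, df n − 1.

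| n per arm | b (SD) | Between-arm noncentrality | Between-arm rejection rate | Within-VR noncentrality | Within-VR rejection rate |
|---|---|---|---|---|---|
| 8 | 0.2 | 0.632 | 9.1% | 0.894 | 12.2% |
| 8 | 0.3 | 0.949 | 14.3% | 1.342 | 21.4% |
| 10 | 0.2 | 0.707 | 10.3% | 1.000 | 14.6% |
| 10 | 0.3 | 1.061 | 17.1% | 1.500 | 26.9% |

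**With the planned test.** Section 5.2 names Mann-Whitney for the between-arm comparison. Simulated on change with r = 0.8 and 10 per arm, it rejects in about 9% to 15% of trials for the same shifts, slightly below the t-test.

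**Sensitivity to the assumed correlation.** With b = 0.2, 10 per arm and 20,000 simulated trials per setting, Mann-Whitney on change rejects in 8%, 10% and 23% of trials for r = 0.70, 0.85 and 0.95. The answer depends heavily on an input the protocol does not supply.

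**Checks**

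- With no shift, Mann-Whitney on change rejects in 3.8% to 4.4% of trials and the within-VR test in 4.7% to 5.2%.
- Mann-Whitney on T1 alone stays at about 4% whatever the shift.
- With the shift reversed (VR scores too high at T0, r = 0.8), significant results favouring VR on change fall from about 2% to under 1%. The bias then runs against VR.

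**The case against.** The strongest reply is that section 3.3 says when patients are assigned, not when patients or raters are told, and that the list is held by someone who does not assess patients. Section 7 also locates assessment expertise in university departments distinct from the treating unit. This stands in part. Custody of the list is a real safeguard and should be credited, but it restricts access to the list. It does not keep an assignment already made from the patient, the treating team or the rater.

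Other objections also stand and limit the point:

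- A reader might infer that every analysis is compromised. The protocol does not support that: satisfaction, demographics and a T1-only Mann-Whitney test do not use T0.
- A reader might infer that a baseline-adjusted treatment difference is biased by the full shift. The protocol specifies no such analysis. In one, the shift would enter multiplied by the T0-T1 slope (0.8 under the assumption above), not in full.
- A reader might take the 9% to 17% as this trial's false-positive rate. It is not. The shift, its direction and the correlation are all assumed.
- The within-VR rates are weaker evidence than they look. An uncontrolled pre/post comparison in one arm is not protected by randomisation in any case, and other pre/post influences would remain after reordering.
- Blinding of raters at T1 is a separate matter and adds no weight here.

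**Conclusion.** The point holds as an avoidable exposure to bias, not as a demonstrated error rate. The order in section 3.3 is explicit and nothing elsewhere reverses it. The primary comparison uses T0, as does any between-arm comparison of change. Several of the scales could respond to knowledge of the arm. Size and sign are unknown: the illustrative rise from 5% to about 9% to 17% rests on an assumed correlation of 0.8 and an assumed downward shift of 0.2 to 0.3 SD in VR baselines.

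A reader might go further and call this fatal to the trial. The documents do not support that. This is a 20-patient pilot meant to estimate variation for a later study, a partial safeguard is stated, and a T1-only between-arm comparison would survive. It should be fixed before enrolment, because a baseline collected after the arm is known cannot be repaired in the analysis.

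**What to change.** In section 3.3, replace the closing sequence with: consent; eligibility tests; complete T0; release of the allocation by the investigator who keeps the list; start of treatment. State that the allocation is not disclosed to the patient, the treating team or the T0 rater until T0 is complete.

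The cost is a rewording of two sentences. No patients or visits are added, since section 5.1 already allows a week for T0. The small downside is that treatment slots are booked after T0 instead of before it.
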